At 24 weeks, 41.9% of patients treated with ruxolitinib experienced a 35% or greater reduction in spleen volume compared to 0.7% of patients receiving placebo ($P < 0.0001$). 45.9% of ruxolitinib treated patients regardless of their JAK2 mutational status experienced a $\geq 50\%$ improvement in constitutional symptoms as compared to 0.7% in the placebo group. Survival analysis on extended ruxolitinib therapy with a mean follow up of 52 weeks showed a statistically significant reduction in death with a hazard ratio of 0.499 (0.254, 0.98) and a probability of survival compared to placebo of 0.98 vs 0.90 and 0.84 vs 0.77 in patients with a baseline hemoglobin $>10\text{g/dL}$ and $<10\text{g/dL}$, respectively (27). In further subset analysis, patient age ≤ 65 years appeared to have a survival benefit over > 65 years of age with a HR 0.22 (0.06,0.84) with ruxolitinib therapy.

The drug therapy was uniformly ineffective in reversing histopathological abnormalities in the peripheral blood or marrow, eliminating marker cytogenetic abnormalities or reducing the

JAK2V617F allele burden to a degree associated with tyrosine kinase inhibitor therapy of BCR/ABL1 for chronic myeloid leukemia. The other limitation of the agent that has been the rapid return of splenomegaly following discontinuation of the drug and the occasional occurrence of life threatening syndromes attributed to the rapid elevation of cytokines. This “ruxolitinib withdrawal syndrome” has been described in 5 of the 47 MF patients treated at Mayo Clinic that had rapid discontinuation and the authors advise tapering the drug when possible in addition to upfront discussion with the patient regarding this potential drug associated serious adverse event (28).

The *COntrolled Myelofibrosis Study with ORal JAK2 inhibitor Treatment COMFORT-2* study was a randomized (2:1), Novartis sponsored, open-label phase III clinical trial conducted in nine European countries comparing ruxolitinib to best available therapy (BAT) (29). Hydroxyurea (46.6%), steroids (16.4%) and supportive therapy (32.9%) comprised the BAT arm. At a median age of 66 years, 219 patients with intermediate-2 or high risk MF were randomized (146 ruxolitinib, 73 BAT).

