7.2.2.3 MRI/CT

MRI or CT will be performed for the purpose of measuring spleen volume. This will be performed at baseline (screening), C4D1 \pm 1 week, and C6D29/C7D1 \pm 1 week, or when possible when the patient permanently discontinues study treatment, whichever comes first. Patients achieving a 35% reduction in splenic volume will be considered responders, otherwise they will be considered non-responders. These patients will also continue to be assessed by physician palpation of splenic length at the start of each cycle. MRI is the preferred method for obtaining spleen volume data, however, CT scans may be performed at the visits where MRI would be conducted if the subject is not a candidate for MRI, or if MRI

is unavailable. The imaging modality used at baseline (MRI or CT) to assess spleen volume should be kept constant throughout the trial period for a given patient, unless a new contraindication to the use of MRI occurs.

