10.4.2.2 Dose expansion

The cohort of 6 patients at the MTD and/or RPTD will be expanded by an additional 16 patients in order to further assess safety and tolerability. Thus the number of patients treated at the MTD and/or RPTD will be 22, which ensures that there is a 90% chance to detect any AE with a 10% incidence rate among patients treated at the MTD and/or RPTD. During this phase of the study, further defining of the biological activity of this combination will be explored. The primary endpoint of this portion of the trial is response rate by IWG-MRT criteria. We hypothesize a response rate of >40% in treated patients at C6D28 will constitute a positive primary endpoint. A positive response by IWG-MRT criteria includes SD, CI, PR, or CR. Since preclinical studies suggest a synergistic effect of the two agents in combination, we would expect a spleen response rate (>35% reduction in spleen volume by MRI or >50% reduction in palpable spleen) of >30% as was assumed in the COMFORT study. Since the proportion of patients obtaining this efficacy endpoint was 42%, we will have a target response for this secondary endpoint of >50%, and this will be reported in a descriptive manner.

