10.6 Exploratory objectives

The following exploratory efficacy objectives will be included on the study:

10.6.1 To assess preliminary efficacy of the combination of RUXOLITINIB and PANOBINOSTAT by physician palpation in all dosing cohorts

Spleen measurements by palpation will be obtained with a primary emphasis on the change in measurements from baseline to Week 12. Descriptive statistics will be provided for the spleen length and percent change from baseline over time. The proportions of patients with at least a 50% reduction in palpable spleen length at any time point, at week 12 and at week 24 will be summarized. This analysis will be done separately on patients in every dosing cohort, as well as, on the pooled patients, in the escalation phase.

10.6.2 To assess the preliminary efficacy at the MTD and/or RPTD by the use of MRI/CT

The endpoint for this objective will be the volumetric reduction in spleen size from baseline to Week 12 (or end of study, whichever comes early), as assessed by MRI/CT. The analysis will be restricted to patients in the expansion phase, who are dosed at the MTD and/or RPTD. Responders (defined as those achieving at least 35% reduction in splenic volume (compared to baseline), at week 12 or end of study, whichever comes first), will be summarized in terms of percentage rates of response, along with 95% confidence intervals. An **exact binomial confidence interval** (implemented using SAS procedure FREQ with EXACT statement for one-way tables) will be calculated (Clopper 1934). Descriptive statistics for the volumetric reduction in spleen size and percent change (from baseline) at the end of week 24 will also be provided. Since preclinical studies suggest a synergistic effect of the two agents in combination, we would expect a spleen response rate (>35% reduction in spleen volume by MRI) of >30% as was assumed in the COMFORT study. Since the proportion of patients obtaining this efficacy endpoint was 42% in COMFORT-1, we will have a target response for this secondary endpoint of >50%, and this will be reported in a descriptive manner.

10.6.3 To assess (preliminary) efficacy of the combination of RUXOLITINIB and PANOBINOSTAT by bone marrow biopsy in all dosing cohorts

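### Section 10.6.2 reads spleen-volume response at Week 12 or at an undefined earlier end of study, so a patient who stops before Week 12 with a 35% reduction can be counted as a responder

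*Combined protocol and SAP*

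**What the plan says.** Section 10.6.2 gives the timing twice. The endpoint is the "volumetric reduction in spleen size from baseline to Week 12 (or end of study, whichever comes early), as assessed by MRI/CT", and patients with at least a 35% reduction "at week 12 or end of study, whichever comes first), will be summarized in terms of percentage rates of response", with an exact binomial 95% interval. On the population it says: "The analysis will be restricted to patients in the expansion phase, who are dosed at the MTD and/or RPTD". On the target it says: "we will have a target response for this secondary endpoint of >50%, and this will be reported in a descriptive manner". The target is motivated by the 42% seen in COMFORT-1.

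Section 7.2.2.3 places scans at screening, C4D1 and the end of cycle 6 (the last two within a week either way), "or when possible when the patient permanently discontinues study treatment, whichever comes first". It treats anyone who does not reach 35% as a non-responder.

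Three other places bear on what end of study means or how early leavers are handled:
- Section 7.1.5 puts the closing visit at least 30 days after the last dose. Its listed content is clinical history, examination, blood tests and an ECG, with no MRI or CT.
- The Glossary dates the end of participation to the later of the final evaluation visit and treatment discontinuation.
- Section 10.4.3, on missing values, covers enrolment of additional patients and continuing events. It does not say how withdrawal before Week 12 is scored.

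**The concern.** The stated objective is the change from baseline to Week 12 at the recommended dose, and C4D1 follows three 28-day cycles (84 days, or 12 weeks) of combination therapy. If an earlier exit scan is used instead, the quantity becomes response at the last scan up to Week 12. A patient who could not stay on the combination may then be scored as a success.

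An exit scan need not describe the spleen at Week 12: Section 1.3.3 reports "rapid return of splenomegaly following discontinuation of the drug", meaning ruxolitinib. Early exits are foreseen, since Sections 6.2.5 and 6.2.8 list toxicities that end participation. A 35% reduction by then is possible, because the baseline scan precedes the 28-day ruxolitinib induction (Section 4.1).

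At stake is how the rate reads against its target. The difference between scoring rules grows with the number of early stoppers, so it matters most if the combination is poorly tolerated. The plan draws the distinction elsewhere: for palpation, Section 10.6.1 reports response at any time, at Week 12 and at Week 24 separately.

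**Working it through.** **1. The plan's own figure.** Section 10.4.2.2 adds 16 patients to 6 for a total of 22, "which ensures that there is a 90% chance to detect any AE with a 10% incidence rate". Check: 1 − 0.9^22 = 0.9015, which reproduces. It concerns adverse events. The spleen endpoint has no sample-size figure, and the end of Section 10.8 rules out formal tests and power analysis for secondary variables.

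**2. Weight of one patient.** 1/22 = 4.5 points. If only the 16 added patients count, 1/16 = 6.25, or 6.3 points.

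**3. Where the target falls** (Clopper-Pearson 95% intervals).

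| Responders | Rate | 95% interval | Above 50%? |
|---|---|---|---|
| 11/22 | 50.0% | 28.2 to 71.8 | no |
| 12/22 | 54.5% | 32.2 to 75.6 | yes |
| 8/16 | 50.0% | 24.7 to 75.3 | no |
| 9/16 | 56.3% | 29.9 to 80.2 | yes |

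**4. Effect of the rule.** Let d be the share of patients who stop before Week 12, p the Week-12 response rate among those still on treatment, and q the share of early stoppers with at least a 35% reduction on a discontinuation scan (unscanned stoppers count as not reaching it).
- Rate with the discontinuation scan accepted: (1 − d)p + dq
- Rate with early withdrawal as non-response: (1 − d)p
- Difference: dq, which is never negative

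**5. Size under assumed values.** The documents give none of d, p or q. The difference in points is:

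| d | q = 0 | q = 0.25 | q = 0.50 |
|---|---|---|---|
| 10% | 0 | 2.5 | 5 |
| 20% | 0 | 5 | 10 |
| 30% | 0 | 7.5 | 15 |

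Two examples with d = 0.20 and q = 0.50, giving the binomial chance of at least 12 responders in 22:
- p = 0.60: 0.48 + 0.10 = 58% against 48%; chance 0.71 against 0.34.
- p = 0.50: 0.40 + 0.10 = 50% against 40%; chance 0.42 against 0.12.

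**6. A different comparator.** Suppose the early stoppers would have responded at rate p had they stayed on treatment. The plan's rate then differs from p by d(q − p), which is negative whenever q is below p. With p = 0.60, d = 0.20 and q = 0.25 the plan gives 0.48 + 0.05 = 53%, seven points below 60%.

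**7. What end of study could mean.** Under Section 7.2.2.3 the early value is a scan at discontinuation, and step 4 applies. Under Section 7.1.5 and the Glossary it would be read at a visit a month or more off drug at which no scan is listed. Given the rebound in Section 1.3.3, a transient responder could then look like a non-responder. Section 10.6.2 does not choose between these.

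**The case against.** The strongest reply is that Section 10.6.2 says end of study, not discontinuation scan. On the Glossary and Section 7.1.5 reading, step 4 does not apply and the effect could run the other way. This stands in part: counting the early stopper as a responder depends on reading Section 10.6.2 with Section 7.2.2.3. That reading is natural, because Section 7.2.2.3 is the only text reviewed that arranges a scan at early stopping, but it is not stated.

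Other points that stand:
- Sections 7.2.2.3 and 10.1.1 (all dosed patients form the primary efficacy set) already point to unscanned patients being non-responders. Selective availability of the exit scan therefore does not add to the upward effect.
- The benchmark is a later reading: "At 24 weeks, 41.9% of patients treated with ruxolitinib experienced a 35% or greater reduction in spleen volume". Scoring at C4D1 leaves that mismatch in place. The documents do not say how COMFORT-1 scored early stoppers, so it cannot be shown that this rule is more lenient than the benchmark's.
- The size is assumed. If 10% stop early and 30% of those reach 35%, then 3% of patients are affected, and the chance that none of 22 is affected is 0.97^22 = 0.51. The dose holds and reductions in Section 6.2.7 may also keep patients on study to Week 12.
- One patient can move any cut-off with 22 patients, and the interval at 12/22 already spans 32% to 76%.

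A reader might infer that the reported rate is biased upward outright, or that the trial would wrongly declare success. The documents support neither. The direction is certain only against a rate that scores withdrawal as failure, and no test or decision is tied to the target.

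**Conclusion.** The concern holds in a limited form. With the discontinuation scan taken as the early reading, a patient who stops before Week 12 with at least a 35% reduction is a responder, and nothing in the plan scores that withdrawal as non-response. Relative to a rate that does, the excess is dq: zero or positive, 4.5 points per such patient with 22 or 6.3 with 16. One such patient can move 11/22 to 12/22 and across the target.

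The total is unknown. It is zero if no early stopper reaches 35%, and 2.5 to 15 points over the non-zero values of q assumed above. Against the rate these patients would have had on continued treatment, the direction is open.

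The firmer finding is that end of study is undefined for this endpoint, and the Glossary and Sections 7.1.5, 7.2.2.3 and 10.6.2 need reconciling. The matter is minor: the endpoint is descriptive, and the phase II primary endpoint (IWG-MRT response at the end of cycle 6) is unaffected.

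**What to change.** In Section 10.6.2:
- Define a Week-12 responder as a patient with at least a 35% volume reduction on the C4D1 scan (within one week either way).
- Count patients who discontinued earlier, or who have no scan in that window, as non-responders. This agrees with the responder rule in Section 7.2.2.3.
- State the denominator: all 22 patients dosed at the RPTD, or the 16 added in the expansion.
- Report the present whichever-is-first version as a supportive analysis, and define end of study for it consistently with the Glossary and Sections 7.1.5 and 7.2.2.3.
- State that the 42% behind the target is a Week-24 rate.

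The cost is wording only, with no new scans. The downside is a possibly slightly lower reported rate on a descriptive endpoint. The Week-24 benchmark mismatch remains but is disclosed.

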10.6.5 To evaluate changes in packed red blood cell transfusion dependence

The proportion of patients who are transfusion dependent, as well as, the proportion of patients whose transfusion status (dependent or independent) changed (from dependent to independent or vice versa - (Gale 2011)) at each cycle will be tabulated with summary statistics.

- A patient will be defined as transfusion dependent at baseline if he or she received 2 or more units of red blood cell products during the 12 weeks prior to first study treatment administration
- New onset of transfusion dependence will be defined as the use of 2 or more units of red blood cell products during the last 12 weeks prior to end of study for patients who were not transfusion dependent at Baseline
- New transfusion independence will be defined as no use of red blood cell products during the last 12 weeks prior to the end of study for patients who met the definition of transfusion dependence at baseline.

10.7 Interim analysis

There is no plan for an interim analysis.

10.8 Sample size calculation

For a cohort size of 3-6 patients, and assuming that escalation happens all the way up to and including cohort 7, and all patients are evaluable, the maximum total sample size will be 58 patients. The minimum sample size will be 33, which will occur if DLT is observed in the

first 2 patients in cohort 4a. In such a case, cohort 3 would add another 3 patients to bring its total to 6. An additional 16 patients for Phase II would bring the total to $12 + 2 + 3 + 16 = 33$. If MTD and/or RPTD is achieved earlier, the sample size will be smaller. This is a Phase I study with a 3 + 3 dose-escalation scheme, first escalating Panobinostat followed by escalation of Ruxolitinib and finally an escalation of the frequency of administration of Panobinostat, as described above. In each escalation, the probabilities of escalating to the next dose after only 3 patients, and of escalating to the next dose after 3 or 6 patients, as a function of the probability of a Dose Limiting Toxicity (DLT) for a given dose, are shown in the table below [Rubinstein and Simon, 2003] :

Probability of DLT for given dose level	.05	.10	.20	.30	.40	.50	.60
Probability of continuing escalation after only 3 pts	.86	.73	.51	.34	.22	.13	.06
Probability of continuing escalation after 3 or 6 pts	.97	.91	.71	.49	.31	.17	.08

Since this is an adaptive design, it is not known exactly how many patients will be required in the trial. If all proposed doses of both drugs, as well as both proposed frequencies of administration for Panobinostat, are such that the trial does not terminate due to DLTs, it is possible that a maximum of 42 patients will be enrolled in Phase I, given the history of enrollment up through cohort 3. Since only 12 patients have been enrolled up through cohort 3, if 6 patients are required for each cohort up through cohort 7, a total of 42 patients will have contributed to Phase I. An additional 16 patients for Phase II would bring the maximum number of patients to $42 + 16 = 58$.

In the Phase II expansion study, 22 patients treated at the MTD and/or RPTD, ensuring that there is a 90% power, at an alpha level of 5%, to detect any AE with a 10% incidence rate among patients treated at the MTD and/or RPTD. However few or many patients are enrolled in Phase I, the 6 patients at the RPTD will be carried forward as the initial 6 patients in the Phase II study (Messer et al., 2010).

All inferential statistical analyses for secondary variables will be based on an estimation approach. There will be no formal testing of hypotheses for these variables, and no power analysis has been done.

11 Ethical considerations and administrative procedures

11.1 Regulatory and ethical compliance

This clinical study was designed, shall be implemented and reported in accordance with the ICH Harmonized Tripartite Guidelines for Good Clinical Practice, with applicable local regulations (including European Directive 2001/20/EC and US Code of Federal Regulations Title 21), and with the ethical principles laid down in the Declaration of Helsinki.

11.2 Responsibilities of the investigator and IRB/IEC/REB

The protocol and the proposed informed consent form must be reviewed and approved by a properly constituted Institutional Review Board/Independent Ethics Committee/Research

Ethics Board (IRB/IEC/REB) before study start. A signed and dated statement that the protocol and informed consent have been approved by the IRB/IEC/REB must be given to Novartis before study initiation.

11.3 Informed consent procedures

Eligible patients may only be included in the study after providing written (witnessed, where required by law or regulation), IRB/IEC/REB-approved informed consent, or, if incapable of doing so, after such consent has been provided by a legally acceptable representative of the patient. In cases where the patient's representative gives consent, the patient should be informed about the study to the extent possible given his/her understanding. Informed consent must be obtained before conducting any study-specific procedures (i.e. all of the procedures described in the protocol). The process of obtaining informed consent should be documented in the patient source documents. The date when a subject's Informed Consent was actually obtained will be captured in their eCRFs.

Women of child bearing potential should be informed that taking the study medication may involve unknown risks to the fetus if pregnancy were to occur during the study and agree that in order to participate in the study they must adhere to the contraception requirement for the duration of the study. If there is any question that the patient will not reliably comply, they should not be entered in the study.

11.4 Discontinuation of the study

Novartis reserves the right to discontinue this study under the conditions specified in the clinical study agreement. Specific conditions for terminating the study are outlined in Section 4.4.

11.5 Publication of study protocol and results

The investigators assure that the key design elements of this protocol will be posted in a publicly accessible database such as clinicaltrials.gov. In addition, upon study completion and finalization of the study report the results of this study will be either submitted for publication and/or posted in a publicly accessible database of clinical study results.

11.6 Study documentation, record keeping and retention of documents

The investigators will maintain appropriate medical and research records for this trial, in compliance with Section 4.9 of the ICH E6 GCP, and regulatory and institutional requirements for the protection of confidentiality of subjects.

Source data are all information, original records of clinical findings, observations, or other activities in a clinical trial necessary for the reconstruction and evaluation of the trial. Examples of these original documents and data records include, but are not limited to, hospital records, clinical and office charts, laboratory notes, memoranda, subjects' diaries or evaluation checklists, pharmacy dispensing records, recorded data from automated instruments, copies or transcriptions certified after verification as being accurate and

complete, microfiches, photographic negatives, microfilm or magnetic media, x-rays, and subject files and records kept at the pharmacy, at the laboratories, and medico-technical departments involved in the clinical trial.

Data collection is the responsibility of the clinical trial staff at the site under the supervision of the site Principal Investigator. The study eCRF is the primary data collection instrument for the study. The investigator should ensure the accuracy, completeness, legibility, and timeliness of the data reported in the eCRFs and all other required reports. Data reported on the eCRF, that are derived from source documents, should be consistent with the source documents or the discrepancies should be explained. All data requested on the eCRF must be recorded. Any missing data must be explained. Any change or correction to an eCRF should be explained (if necessary) and should not obscure the original entry. An audit trail will be maintained by the system.

The investigator/institution should maintain the trial documents as specified in Essential Documents for the Conduct of a Clinical Trial (ICH E6 Section 8) and as required by applicable regulations and/or guidelines. The investigator/institution should take measures to prevent accidental or premature destruction of these documents.

Essential documents (written and electronic) should be retained for a period of not less than fifteen (15) years from the completion of the Clinical Trial unless Sponsor provides written permission to dispose of them or, requires their retention for an additional period of time because of applicable laws, regulations and/or guidelines

